1.0 Study Summary*

This is a pilot study of randomized clinical trial of Parent Acceptance and Commitment Therapy vs. an attention-control condition (placebo) for improving the mental health of parents of children with pediatric feeding disorder. The primary aims of this study are to evaluate feasibility and proof-of-concept.

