2.0 Objectives*

2.1 Purpose, specific aims or objectives: Primary Aim: Test the hypothesis that PACT will result in clinically meaningful reductions in Mental Health(MH) problems among parents of children with Pediatric Feed Disorder (PFD) and identify factors that impact the feasibility of intervention delivery. This pilot study will involve conducting recruitment procedures for 4 months (or until parent N=30). Participants will be parents of 2- to 6-year-old children with PFD in outpatient treatment for their PFD. Parents will be randomly assigned to PACT or an attention control condition (control). Secondary aim: Test the hypothesis that PACT-F will result in clinically meaningful improvements in parent use of positive behaviors at meals, as measured through an observation of a representative mealtime.

2.2 Hypothesis: We will test the hypothesis that PACT results in clinically meaningful change in parent stress and anxiety, and parent use of positive mealtime behaviors, using the Reliable Change Index (RCI; success defined as $RCI > 1.96$). We anticipate that these procedures will be feasible, with feasibility success defined as recruitment rate above 60%, and retention, assessment completion, and intervention completion rate above 80%. Mixed methods data collection will identify factors that impact 1) recruitment rate (qualitative surveys, % meeting inclusion criteria, # of contact attempts), 2) retention rates (qualitative surveys, baseline characteristics; treatment group), 3) assessment completion rate (qualitative surveys, measure type), and 4) treatment completion rate (qualitative surveys, scheduling, treatment location).

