Acceptance and Commitment Therapy (ACT) has the Potential to Radically Improve the Uptake of Parent MH Interventions and is Therefore Ideal for Parents of Children with PFD. ACT is a transdiagnostic treatment approach that is effective in treating a wide range of adult MH problems. Emerging studies have found it can be effective in as few as one session.²⁷ ACT focuses on changing how a person perceives and responds to negative thoughts and feelings, rather than focusing on challenging and eliminating these thoughts and feelings which can be more time intensive. ACT recently was adapted for parents of children with neurodevelopmental disorders (PACT), and a series of pilot studies found that PACT meaningfully reduced parent depression and anxiety, and improved child behavioral outcomes, in just 2-sessions.^{21,26,27} However, PACT has never been tested in a PFD population (nor has it been tested for problems other than anxiety and depression). If effective with parents of children with PFD, this brief treatment could radically increase the potential for uptake of parent MH treatment in PFD treatment clinics nationally.

Treatment Adaptations and Feasibility Testing are Critical Next Steps. In order to optimize the treatment for parents of children with PFD, our team has adapted PACT to meet the needs of parents of children with PFD using formative research methods (IRB# 00002321). Feasibility testing and proof-of-concept testing are the essential next steps before proceeding to an efficacy study.

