28.0 Statistical Analysis*

10.1 Data will be analyzed using SPSS. We will conduct descriptive statistics to evaluate the research endpoints of this study. We will

SHORT TITLE:

conduct correlations between demographic factors and endpoints to evaluate relationships that may influence these endpoints.

10.2 Quantitative Feasibility Analyses. Descriptive statistics (frequency counts, %s) will determine recruitment, retention, assessment, and intervention delivery success and will be compared to identified benchmarks of success (recruitment rate above 60%, and retention, assessment completion, and intervention completion rate above 80%). Factors that may impact success will be evaluated in relation to these outcomes using t- and chi-squared tests.

10.3 Qualitative Feasibility Analyses. Parent free text responses to feasibility questions will be imported into NVivo 12 software for coding. A coding tree will be developed a priori and periodically revised to include relevant inductive codes as emergent themes arise. Qualitative responses will then be double coded by PI and a graduate research assistant. Interrater reliability will be coded, with the goal of achieving 80% interrater reliability. PI mentor will provide direct supervision for data collection and analysis.

10.4 Proof of concept analyses. We use the Reliable Change Index (RCI; success defined as $RCI > 1.96$) to determine if there is a reliable signal of change for participants who are in the PACT (active treatment) group from baseline to post-treatment and follow-up. The RCI is a psychometric criterion used to evaluate whether change is significant at the level of the individual. An RCI will be calculated for each participant in the PACT (active treatment) group, using the following formula: $RCI = \text{observed difference score between measurements} / \text{standard error of measurement of the difference}$. We will assess proof of concept for change in parent stress, parent anxiety, and parent behavior at meals (measured by the DINE).

10.5 Given the feasibility and proof-of-concept nature of this study, we are interested in seeing if these study procedures are feasible and if there are meaningful improvements (e.g., several points of improvement on rating scales) rather than statistical significance. The sample size was therefore selected to ensure that a large enough group of participants can be evaluated to be reflective of a heterogeneous group of parents.

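### The hypothesis that PACT causes improvement is tested with Reliable Change Index values from the PACT arm alone, leaving the randomised control out of the comparison

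*Combined protocol and SAP*

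**What the plan says.** Section 2.2 states the hypothesis in causal terms: "We will test the hypothesis that PACT results in clinically meaningful change in parent stress and anxiety". The secondary aim in section 2.1 does the same for mealtime behaviour: "PACT-F will result in clinically meaningful improvements in parent use of positive behaviors at meals". Section 1.0 presents the study as a randomised comparison with an attention control, and section 8.0 plans 20 parents on active treatment and 10 on control.

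The analysis that answers the hypothesis is item 10.4 of section 28.0. It restricts itself to one arm twice. The target is a "reliable signal of change for participants who are in the PACT (active treatment) group", from baseline to post-treatment and follow-up, and then: "An RCI will be calculated for each participant in the PACT (active treatment) group". Success is an RCI above 1.96. The outcomes are stress, anxiety and parent behaviour at meals scored from the DINE.

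Elsewhere in section 28.0, item 10.1 says "We will conduct descriptive statistics to evaluate the research endpoints of this study" and adds correlations with demographic factors; it names no comparison of arms. The t- and chi-squared tests in item 10.2 concern factors that may affect feasibility. Treatment group is named as an analytic factor once, in section 2.2, for retention.

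**The concern.** The question is about cause, the design has a randomised control that could address it, and the stated analysis does not use that control. The RCI judges whether one person's change is larger than measurement error would produce. It says nothing about why the person changed.

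This design has other routes to improvement. Every child is in outpatient feeding treatment (section 7.0). Every parent has two 90-minute sessions with a trained interventionist (section 6.0). Every parent enters with an elevated score on at least one mental health measure (section 7.0), so some fall towards the mean is possible on those scales. Under item 10.4 as written, improvement from any of these sources would be read as a PACT signal.

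Proof of concept is one of the two primary aims in section 1.0, and section 3.0 makes it a step towards a larger trial: "Feasibility testing and proof-of-concept testing are the essential next steps before proceeding to an efficacy study". A signal that cannot be told apart from background improvement is a weak basis for that step.

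**Working it through.** **Sample size.** The only sample-size arithmetic in the plan is in section 8.0: 80 consented, about 60% not eligible. 80 × (1 − 0.60) = 32, consistent with 30 randomised. No power or precision figure is given for any clinical outcome, so there is none to reproduce.

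**Is the contrast planned anywhere?** Items 10.1, 10.2, 10.4, 10.5 and 10.6 of section 28.0 and sections 2.1, 2.2 and 4.0 contain no control-arm RCI and no arm difference in stress, anxiety or DINE parent behaviour.

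**Would the data exist?** Yes. Section 4.0 schedules the questionnaires and mealtime recordings at baseline, post-intervention and 3 months for parents without restriction by arm. Section 10.0 offers controls the active treatment only after the 3-month follow-up, so both follow-up contrasts are intact.

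**How many parents could pass with no PACT effect?** The documents give no reliability and no expected background change, so both are assumptions here. In baseline SD units, with reliability r and background improvement d shared by all parents:

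- standard error of the difference: SEd = √(2(1 − r)), which is 0.632 at r = 0.80 and 0.447 at r = 0.90
- P(RCI > 1.96) = 1 − Φ(1.96 − d/SEd)

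| d (SD) | r = 0.80: share; of 20; of 10 | r = 0.90: share; of 20; of 10 |
|---|---|---|
| 0 | 2.5%; 0.5; 0.25 | 2.5%; 0.5; 0.25 |
| 0.1 | 3.6%; 0.7; 0.36 | 4.1%; 0.8; 0.41 |
| 0.2 | 5.0%; 1.0; 0.50 | 6.5%; 1.3; 0.65 |
| 0.3 | 6.9%; 1.4; 0.69 | 9.9%; 2.0; 0.99 |
| 0.5 | 12.1%; 2.4; 1.21 | 20.0%; 4.0; 2.00 |

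These are for one scale at one time point. If both arms share the same background improvement, their expected rates are equal and the expected difference is 0. Item 10.4 would show only the 20-parent count.

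**Regression to the mean.** This was simulated with no treatment effect, selecting the top 40% on a single normally distributed measure. With pure measurement error and r from 0.7 to 0.9, 3.8% to 4.7% pass (0.8 to 0.9 of 20). If the RCI uses a reliability of 0.85 to 0.90 while the true retest correlation is 0.5 to 0.7, 20% to 28% pass (4.1 to 5.5 of 20). Actual eligibility is elevation on any one of several measures, and the DINE is not used for selection, so this is a range for the mental health scales and not a prediction.

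**What would the control add at 20 against 10?** Newcombe 95% intervals for PACT minus control:

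- 8/20 against 2/10: 0.40 − 0.20 = +20 points (−16 to +46)
- 4/20 against 2/10: 0.20 − 0.20 = 0 points (−33 to +26)

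For a difference in mean change, the approximate 95% half-width is 1.96 × √(1/20 + 1/10) = 0.76 SD, or 1.96 × √(1/16 + 1/8) = 0.85 SD with 80% retained in each arm.

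**The case against.** The strongest reply is that this is a pilot. Item 10.5 says the interest is in meaningful improvement and sets statistical significance aside, the sample size was not chosen for an arm contrast, and ten controls cannot settle anything. That justifies having no powered test. It does not justify having no control estimate when the hypothesis is worded causally, and the change proposed here asks for estimates only.

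Second, item 10.1 does not exclude controls, so their outcomes might be tabulated. That is fair: the gap is a control RCI and a named contrast, not a ban on describing control data. But item 10.4 carries the success criterion, and it is limited to PACT. Adding the comparison later would lose no data, but it would then be a choice made after outcomes could have been seen.

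Third, the RCI is an individual-level criterion, and the plan sets no share of parents at which PACT succeeds. This stands, and the fix does not supply such a rule. Likewise, the plan names a DINE parent-behaviour subscale without giving the score or reliability an RCI needs. That must be settled whichever arms are analysed.

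Fourth, the illustrative rates rest on assumed inputs, with the largest (4.0 of 20) at the most extreme pair in the table. Also true. The mismatch between hypothesis and analysis does not depend on them.

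**Conclusion.** The concern holds and should be corrected before outcomes are examined. Followed as written, item 10.4 is a within-arm analysis offered as the test of a between-arm causal hypothesis, and no other section supplies the missing contrast. The feasibility benchmarks are not affected.

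The size of any distortion is unknown from the documents. If parents would not have improved without PACT, it is small; under the larger assumed drifts, several of the 20 PACT parents could pass with no PACT effect at all. Only the control result can show which case applies, and at 10 controls it will do so imprecisely. It gives context for the PACT result and will not decide the question by itself.

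**What to change.** Replace the PACT-only rule in item 10.4 with wording such as:

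> An RCI will be calculated for every randomised participant with data, in both groups, scored so that positive values mean improvement and using the same standard error of the difference for each scale in both groups. For the PSS, GAD-7 and DINE parent behaviour, at post-treatment and at 3 months, we will report the proportion with reliable improvement in each group and the PACT minus control difference with a 95% confidence interval. These differences are estimates, not confirmatory tests. The PACT result will be presented and interpreted alongside the control result, and change in the PACT arm alone will not be described as an effect of PACT.

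Differences in mean change with intervals could be added, to avoid relying only on a dichotomy.

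If the team prefers to keep a PACT-only RCI, the minimum is to reword sections 2.1 and 2.2 so that they refer to change observed within the PACT arm. That removes the mismatch but leaves the control outcomes unused.

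The cost is one paragraph and one more table column, with no extra participants, visits or measures. The downside is that the signal may look less favourable and the intervals will be wide.

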4.0 Study Endpoints

Parents will complete the standard study battery at baseline, post-intervention, and 3-month follow-up.

Quantitative Measures. Feasibility success is defined as recruitment rate above 60%, and retention, assessment completion, and intervention completion rate above 80%.

SHORT TITLE: PACT Study

Demographics. Parents will provide information on their own and child's age, sex/gender, race/ethnicity, education, and socioeconomic status.

- Parent Mental Health (MH) Measures.
 - PHQ-9. A 9-item self-report measure of depressive symptoms. Scores of 10 or more indicate probable depression.
 - GAD-7. A 7-item self-report measure of anxious symptoms. Scores of 10 or more indicate probable anxiety.⁸⁷
 - IES-R. A 22-item self-report measure of posttraumatic stress symptoms. Scores of 33 or more indicate clinically significant posttraumatic stress.
 - PSS. A 10-item self-report measure of perceived stress. Scores of 14 or more indicate clinically significant stress.
 - AAQ-2. A 7-item self-report measure of psychological flexibility and experiential avoidance, which are targets of the behavioral treatment.
- Child Health.
 - PedsQL 4.0 (Generic). A 23-item parent-proxy measure of child quality of life, with versions specific to child age (2-4 years, 5-7 years) that each result in standardized total scores and domain-specific scores of physical functioning, emotional functioning, social functioning, and school functioning.
 - BPFAS. A 35-item parent-proxy report of child mealtime and feeding behavior.
- Qualitative Measures. Qualitative surveys will be completed by parents at the 3-month follow-up, focused on factors that impact feasibility. Feasibility of 1) recruitment procedures, 2) intervention procedures, and 3) measure completion.

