7.0 Inclusion and Exclusion Criteria*

3.1 Eligibility Criteria:

Inclusion Criteria

- 1) Must be a parent aged 18+ (primary caregiver) of 2-6-year-old child with PFD
- 2) Child must be receiving outpatient PFD treatment at CMH
- 3) The parent must have a clinically significant elevation on at least one measure of parent MH (using established clinical cutoffs). Parents will be included regardless of whether the child has a new diagnosis or established diagnoses

Exclusion Criteria

- 1) Parent has significant cognitive impairments
- 2) Parent does not speak English
- Parent unable to obtain high speed internet at home

3.2 Equitable Selection: We are excluding non-English speaking participants because we are providing a behavioral intervention and do not have a translated version of the intervention available. In the future, we hope to translate this

intervention for non-English speaking patients but are unable to do this for the present study.

3.3 Vulnerable Populations: *Check any vulnerable populations that are being targeted for enrollment into the study: (Members of the following populations may not be included as participants in the research unless selected here.)*

 Children/Minors (under 7 years of age)	 CM Employees
 Children/Minors (7-17 years of age)	 CM Students/Residents/ Fellows
 Neonates (infants less than 30 days old)	 Economically or Educationally Disadvantaged Persons
 Neonates of Uncertain Viability (infants less than 30 days old)	 Prisoners
 Non-Viable Neonates (infants less than 30 days old)	
 Wards of the State	
 Fetuses	
 Pregnant Women	
 Adults with impaired decision-making capacity	

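### Parents may enter on any one scale, but the RCI > 1.96 rule on anxiety and stress covers every PACT parent, including any who start too low on that scale to meet it

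*Combined protocol and SAP*

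**What the plan says.** Section 7.0 (3.1) sets the mental health entry rule: "The parent must have a clinically significant elevation on at least one measure of parent MH (using established clinical cutoffs". Section 4.0 gives cutoffs for four scales, so there are four routes in:

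- PHQ-9: "Scores of 10 or more indicate probable depression"
- GAD-7: "Scores of 10 or more indicate probable anxiety"
- PSS: "Scores of 14 or more indicate clinically significant stress"
- IES-R: 33 or more

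The AAQ-2 has no cutoff.

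Section 28.0 (10.4) states: "An RCI will be calculated for each participant in the PACT (active treatment) group". The RCI is the observed change divided by the "standard error of measurement of the difference". Success is RCI > 1.96, and the rule is applied to parent stress, parent anxiety and DINE mealtime behavior. Section 2.2 ties the hypothesis to the same rule. Neither section limits the anxiety or stress RCI to parents elevated on that scale, sets a minimum baseline, or asks how many parents start too low to reach the threshold. No SD, reliability or SEdiff is given for any scale.

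Section 8.0 plans 20 PACT and 10 control parents and expects about 60% of those consented to fail the inclusion criteria.

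**The concern.** Two rules that are reasonable separately do not fit together. Entry asks for distress on any scale, while the success rule asks for a reliable drop on two particular scales. A parent who qualifies on depression or perceived stress may have a GAD-7 of 3 or 4. On a scale with a floor at 0, that parent cannot improve by more than 3 or 4 points, and this may be less than the RCI requires however well PACT works. The same can happen on the PSS for a parent who qualified on another scale.

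Section 3.0 presents this pilot as the step before an efficacy study. If few PACT parents show reliable change on anxiety, readers will want to know whether PACT had little effect or whether many parents had little anxiety to lose. As planned, the report could not separate the two, and the figure would not carry over to a trial with a different entry mix. The block randomization in section 10.0 balances new against established diagnosis, not the qualifying scale.

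**Working it through.** **The plan's own figures.** The two-sided 5% normal quantile is 1.95996, which rounds to the stated 1.96. The screening yield is 80 x (1 - 0.60) = 32, close to the 30 to be randomized. There is no power calculation to reproduce.

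**Required drop.** Take SEdiff = SD x sqrt(2(1 - r)), a scale minimum of 0, and a positive RCI as improvement. Success then needs a drop larger than 1.96 x SD x sqrt(2(1 - r)). SD and r are assumed, because the documents give neither.

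| Scale | Central case | Required drop | Best possible RCI (fall to 0) | Range of required drop |
|---|---|---|---|---|
| GAD-7 | SD 5, r 0.85 | 1.96 x 5 x sqrt(0.30) = 5.37 | from 5: 1.83; from 6: 2.19 | 1.9 to 9.1 (SD 3-6, r 0.70-0.95) |
| PSS | SD 6, r 0.85 | 1.96 x 6 x sqrt(0.30) = 6.44 | from 6: 1.83; from 7: 2.13 | 3.1 to 12.2 (SD 5-8, r 0.70-0.95) |

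In the central cases, a GAD-7 baseline of 0-5 or a PSS baseline of 0-6 cannot succeed. Over the whole range the required drop stays below the scale's cutoff (9.1 against 10, and 12.2 against 14). A parent whose baseline is at or above the cutoff can therefore always succeed. If the sqrt(2) is left out, the required drops are smaller (GAD-7 1.9-5.3, PSS 3.1-7.0 at r 0.8-0.9), but an unreachable zone remains.

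**How many parents.** The model has four equally prevalent, equicorrelated normal scales, with cutoffs placed so that 40% of screened parents exceed at least one. Only the 40% comes from the documents (1 - 0.60, section 8.0). One million draws for each correlation give:

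| Inter-scale correlation | Each scale elevated | Entrants below GAD-7 cutoff | GAD-7 unreachable (SD 5, r 0.85) | PSS unreachable (SD 6, r 0.85) |
|---|---|---|---|---|
| 0.4 | 16% | 60% | 27.5% | about 18% |
| 0.8 | 24% | 39% | 5% | 1.5% |

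Of 20 PACT parents, that is 1 to 6 on the GAD-7 and 0 to 4 on the PSS. With GAD-7 SD 4.5-5.5 and r 0.75-0.90, the required drop runs from 3.94 to 7.62 points and the unreachable share from 1% to 45%. Parents at or above the GAD-7 cutoff make up 40-61% of entrants, or about 8-12 of 20.

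**Effect on a summary.** If k of 20 cannot succeed, the largest possible share with reliable change is (20 - k)/20: 90% for k = 2, 80% for k = 4, 70% for k = 6. With k = 4, a true 50% among parents able to succeed would appear as 0.5 x 16/20 = 40%.

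**Check on the remedy.** Suppose parents are selected on a screening GAD-7 of 10 or more and change is measured from a separate baseline, with retest correlation equal to r (SD 5). About 28-33% then fall below 10 at baseline when r = 0.85. About 2% of the selected parents still cannot succeed at r = 0.85, and 12-15% at r = 0.75. The unreachable count is therefore needed in the by-scale row as well.

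**The case against.** The strongest reply is that the plan does not contain the statistic said to be harmed. Section 28.0 (10.4) describes the RCI as a criterion for the individual. It names no responder proportion and no group-level share that would count as success. A reader might infer that low-baseline parents are formally counted as failures, or that the proof-of-concept test is set up to fail. The documents do not support that: there is no formal group test and no go/no-go threshold. What remains is that individual RCIs will have to be summarised somehow, and any count or share takes in the entry mix.

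A second reply is that analysing everyone admitted is legitimate. Section 28.0 (10.5) wants a heterogeneous group and looks for improvements of several points on rating scales, and 10.1 adds descriptive statistics. A low anxiety response in such a population describes it truthfully. This stands, and it is why the all-PACT result should be kept.

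Third, the size is nearly all assumption. The normal model even puts 10-16% of screened parents below a GAD-7 of 0 at SD 5. This also stands: 1-45% runs from negligible to serious. Nor should the stress scale be read as equally affected. In the same model its share is lower at each correlation, and a parent elevated on another scale would seldom report very low stress; that last is a judgment, not a figure in the documents.

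Finally, selecting on the screening score needs screening and baseline records that can be linked. Section 18.0 pays for the two separately, which suggests two administrations. But section 9.0 (4.4) says no PHI is collected at screening, Addendum E calls the questionnaire database de-identified, and no linkage is described.

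**Conclusion.** The concern holds as a limit on interpretation. For any SEdiff above zero and a scale minimum of 0, some baselines make RCI > 1.96 impossible, and the entry rule lets such parents in through another scale. The mechanism follows from sections 7.0 and 28.0; the number of parents affected cannot be fixed from the documents. The central estimates of 1 to 6 of 20 on anxiety and 0 to 4 of 20 on stress depend on the assumed SDs, reliability, correlations, equal prevalence and normality. The consequence is a success figure that is lowered and hard to interpret, not an invalid test. A cheap addition to the reporting is worth making. Nothing here calls for changing who is enrolled or dropping the planned analysis.

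**What to change.** In section 28.0 (10.4):

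1. Keep the RCI result for all PACT parents.
2. Pre-specify beside it, separately for the GAD-7 and the PSS, the result among PACT parents at or above that scale's cutoff (GAD-7 >= 10, PSS >= 14).
3. In both rows, report the number of parents whose baseline makes RCI > 1.96 unreachable.
4. State the SD and reliability used for SEdiff on each scale.
5. If screening and baseline scores are separate and can be linked, select on the screening score and measure change from baseline. Otherwise select on the baseline score, and note that regression to the mean can inflate change in that row.

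This takes a few lines in the analysis section and one extra row per table, with no new data. The cost is precision: the by-scale anxiety row would rest on about 8-12 of 20 parents before dropout, so its interval is wider. Fixing the row in advance also prevents the denominator from being chosen after the results are seen.

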3.0 Background*

Pediatric Feeding Disorder (PFD) is Prevalent, and Parents are Critical to Treatment Success. One-third of young children, and up to 80% of children with developmental delays, experience pediatric feeding disorder (PFD).¹ PFD is characterized by severely restricted volume or variety of foods and place children at increased risk for malnutrition.^{2,3} PFD is also associated with high financial burden.⁶ Interdisciplinary care to address medical and behavioral components of PFD is essential,^{33,34} and often involves a physician, psychologist, dietitian, and speech or occupational therapists.¹⁸ However, treatment success relies on the implementation of treatment recommendations at home by parents, including structured family meals, positive parent-child interactions at mealtimes, and use of behavioral strategies to reinforce feeding behaviors.³⁵

PFD is a Stressor to Parents. Many parents report distress when their child does not eat well as feeding is essential to survival.¹⁹ Each meal, then (occurring 3-5 times a day), is a

SHORT TITLE: PACT Study

potential stressor for parents of children with PFD. Many parents report “battles” with their children at mealtimes over eating.¹⁹ Parents across the spectrum of child age report similar experiences of mealtime distress.^{12,19,46}

Parents of Children with PFD are at Higher Risk for Mental Health (MH) Problems. Parents of children with PFD are at much higher risk for mental health (MH) problems (depression, anxiety, parenting stress, posttraumatic stress) than their peers,⁷⁻¹⁴ with up to 40% of parents endorsing MH problems.¹² In qualitative interviews, parents report an enduring emotional impact,¹⁹ including that difficulties feeding their young children negatively impacts their identity development as parents.¹⁹ This emotional impact has also been observed biologically, as one study found increases in parent cortisol when feeding their child with PFD.⁴⁷

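### The primary aim covers parent mental health problems in general, but reliable change is planned only for stress and anxiety, and section 2.2 labels it clinically meaningful

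*Combined protocol and SAP*

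**What the plan says.** - **Aim (section 2.1).** The primary hypothesis is that "PACT will result in clinically meaningful reductions in Mental Health(MH) problems".
- **Scope of MH problems (section 3.0).** The Background speaks of "mental health (MH) problems (depression, anxiety, parenting stress, posttraumatic stress". It also says of PACT, on its prior evidence: "nor has it been tested for problems other than anxiety and depression".
- **Entry (section 7.0).** A parent needs a "clinically significant elevation on at least one measure of parent MH (using established clinical cutoffs". Section 4.0 gives cutoffs for four scales: PHQ-9 10, GAD-7 10, IES-R 33 and PSS 14. A fifth measure, AAQ-2, has none.
- **Hypothesis (section 2.2).** The test is whether "PACT results in clinically meaningful change in parent stress and anxiety" (and in positive mealtime behaviors), with success set at RCI > 1.96.
- **Analysis (section 28.0, item 10.4).** "An RCI will be calculated for each participant in the PACT (active treatment) group". The outcomes follow: "We will assess proof of concept for change in parent stress, parent anxiety, and parent behavior at meals". Mealtime behavior is tied to the DINE; stress and anxiety are tied to no scale. The index is described this way: "The RCI is a psychometric criterion used to evaluate whether change is significant at the level of the individual".
- **Other endpoints (item 10.1).** Descriptive statistics, with no further detail.
- **Meaningful improvement (item 10.5).** The stated interest is in meaningful improvement, illustrated by a change of several points on a rating scale, rather than in statistical significance.

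**The concern.** Two things do not line up.

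First, the aim is wider than the analysis that answers it. Depression is among the problems the aim covers, it can be a parent's only reason for entry, and it is one of just two problems on which the Background says PACT has been tested. It still gets no reliable-change result. The same holds for posttraumatic stress if stress is read as PSS. The plan gives no reason for the selection.

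Second, section 2.2 calls a result clinically meaningful when section 10.4 describes it as reliable and psychometric. An RCI above 1.96 says that a change is larger than measurement error would readily produce. It does not say how the parent is doing afterwards.

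At stake is the statement the pilot can make about its primary MH aim, and the signal it hands to the efficacy study that the Background presents as the following step.

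**Working it through.** **1. The threshold.** The two-sided 5% normal quantile is 1.95996, which rounds to the plan's 1.96. With measurement error alone, the chance of exceeding it in the direction of improvement is 2.5% per scale and time point. The number therefore carries statistical content only.

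**2. Coverage.** Four scales have a cutoff, so there are 2^4 − 1 = 15 possible patterns of elevation. Patterns with neither GAD-7 nor PSS elevated number 2^2 − 1 = 3: PHQ-9 only, IES-R only, or both. In these, the qualifying problem has no RCI if stress means PSS. If stress was meant to include IES-R, one pattern remains (PHQ-9 only). The documents do not say how many parents these patterns would contain.

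**3. Reliable against clinical.** Section 10.4 divides the difference score by the standard error of measurement of the difference. In the usual form,

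RCI = fall / [SD × √(2(1 − r))], so the fall must exceed 1.96 × SD × √(2(1 − r)).

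The documents give neither SD nor reliability r, so both are assumed. For GAD-7:

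| Assumed SD | r | Fall needed | RCI, 20 to 12 | RCI, 12 to 7 |
|---|---|---|---|---|
| 4 | 0.80 | 4.96 | 3.16 | 1.98 |
| 4 | 0.85 | 4.29 | 3.65 | 2.28 |
| 4 | 0.90 | 3.51 | 4.47 | 2.80 |
| 5 | 0.80 | 6.20 | 2.53 | 1.58 |
| 5 | 0.85 | 5.37 | 2.92 | 1.83 |
| 5 | 0.90 | 4.38 | 3.58 | 2.24 |
| 6 | 0.80 | 7.44 | 2.11 | 1.32 |
| 6 | 0.85 | 6.44 | 2.43 | 1.52 |
| 6 | 0.90 | 5.26 | 2.98 | 1.86 |

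- A fall from 20 to 12 passes at all nine settings, yet 12 is above the cutoff of 10.
- A fall from 12 to 7 crosses the cutoff but fails the RCI at five of the nine settings.
- For PSS with assumed SD 5 to 7 and the same r, a fall from 26 to 16 gives 10 / (7 × √0.40) = 2.26 up to 10 / (5 × √0.20) = 4.47. It always passes, yet 16 is above the cutoff of 14.

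So reliable change and crossing the cutoff can disagree in either direction.

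**4. Price of adding two scales.** Treating scales as independent at 2.5% each, the chance that a parent with no true change shows at least one false reliable improvement at a given time point is 1 − 0.975² = 4.9% with two scales and 1 − 0.975⁴ = 9.6% with four.

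The 2.5% assumes that baseline is measured separately from screening. The payment table pays for the two separately, which suggests this but does not settle it. If screening scores serve as baseline, selection on an elevation raises the rate. A simulation with four scales and assumed inter-scale correlation of 0.5 to 0.7 gave about 2.9% to 3.5% per scale, and the exact figure moves with the assumed means.

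**The case against.** The strongest reply has four parts.

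- **The hypothesis and the analysis agree.** Sections 2.2 and 10.4 name the same outcomes. A 30-parent pilot may choose two of several constructs, and an entry rule defines a population without obliging the plan to test every screening scale. This stands. A reader might infer that the two sections contradict each other on outcomes; they do not. The mismatch is with aim 2.1, and the selection is unexplained.
- **Nothing goes unanalysed.** PHQ-9 and IES-R are part of the battery at all three time points and fall under 10.1. This also stands. It would be wrong to infer that depression is ignored; what it lacks is a reliable-change result.
- **Section 10.5 gives its own idea of meaningful.** A reliable GAD-7 fall needs 4 to 8 whole points on the assumptions above, which fits an example of several points. This narrows the gap but does not close it: 10.5 offers an example, not a criterion, and step 3 shows both kinds of disagreement.
- **The GAD-7 example is extreme.** With assumed means of 6 to 10 and SDs of 4 to 6, only 0.02% to 4.8% of parents would start at 20 or more. A PSS start of 26 or more is commoner (0.8% to 19.6%, assumed means 14 to 20). The examples show what the criterion permits, not how often it happens.

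A reader might also infer that ending below a cutoff should be the success criterion. The documents do not support that: they specify the cutoffs for entry, not for judging outcome, and whether a large fall ending above a cutoff is meaningful is a judgment the RCI does not settle.

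**Conclusion.** The point holds as a mismatch between a broad primary aim and a narrower proof-of-concept analysis, together with a label in 2.2 that claims more than the index shows. Followed as written, the plan yields no reliable-change result for depression on any reading, and none for posttraumatic stress if stress means PSS.

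A reader might infer that this could turn a go decision into a no-go. It could not: 10.4 sets no target proportion, so what is affected is how the aim is answered and the signal taken forward. It should be fixed, but it does not undermine the feasibility objectives.

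The text comparison needs no assumptions. The illustrations rest on assumed SDs, means and reliabilities, on normality for the baseline shares and error rates, and on independence between scales for the 4.9% and 9.6%.

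**What to change.** **Preferred change, in 10.4:**

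1. Name the instrument for each construct.
2. Calculate the RCI for PHQ-9, GAD-7, IES-R and PSS as well as the DINE, with improvement scored positive.
3. Report the reliable-improvement rate (n/N) per scale and time point.
4. Give the same rate for the control arm as descriptive context, since every parent enters on an elevation and some regression to the mean is expected.

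In 2.2, call RCI > 1.96 reliable change.

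**Minimum alternative:** keep the present outcomes and narrow 2.1 and 2.2 to reliable change in stress and anxiety. This costs nothing analytically, but depression stays without a reliable-change result.

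**Optional:** one descriptive line on how many reliably improved parents also end below the section 4.0 cutoff, not used as a success criterion. A fuller breakdown among parents elevated on each scale is not recommended as the lead. It would bring the MH proportions to 48 (4 scales × 3 summaries × 2 time points × 2 arms), with perhaps 2 to 5 controls in the GAD-7 subset under the assumed means and SDs.

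**Cost.** No new data are needed: the battery is scheduled at all three time points, and controls are offered active treatment only after the 3-month follow-up. MH proportions rise from 4 (2 scales × 2 time points, active arm) to 16 (4 scales × 2 time points × 2 arms). Intervals are wide: 10/20 has an exact 95% interval of 27.2% to 72.8%, and 5/10 of 18.7% to 81.3%, so the control figures are context and not a test. The chance of at least one false reliable improvement per parent rises from about 4.9% to 9.6% per time point, and is somewhat higher if screening scores serve as baseline. The plan should therefore also state which measurement is the baseline.
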